# 1.2 Purpose

The aim of this study is to assess the therapeutic efficacy of secukinumab on the psoriatic skin and to explore the anti-inflammatory (reduction of hepatic inflammation and cell damage), anti-steatotic (reduction of hepatic triglyceride content) and anti-fibrotic (reduction of hepatic fibrosis) effects of secukinumab in patients with psoriasis and coexisting NAFLD.

#### Objectives

Endpoints

, NAFLD = non-alcoholic fatty liver disease, NASH = non-alcoholic steatohepatitis, PASI90 = psoriasis area and severity index, SAE = serious adverse event.

## 3 Study design

This is a randomized, placebo-controlled, double-blind, parallel-group, interventional, multicenter study in patients with moderate to severe plaque psoriasis and coexisting NAFLD. The study consists of 3 periods:

- Screening Period: patient eligibility will be assessed and prohibited medication will be tapered during the max. 4-week Screening Period prior to Randomization/Baseline.
- Treatment Period 1 (Baseline to Week 12): patients will be randomized 2:1 to either receive secukinumab 300 mg s.c. (in 2 × 150 mg PFS) or placebo (in 2 × PFS) at Randomization/Baseline, Week 1, Week 2, Week 3, Week 4 and Week 8.
- Treatment Period 2 (Week 12 to Week 24): starting from Week 12, all patients will receive secukinumab 300 mg s.c. up to Week 20. Patients who were randomized to placebo during Treatment Period 1 will receive secukinumab 300 mg s.c. at Week 12, Week 13, Week 14, Week 15, Week 16 and Week 20. Patients who were randomized to secukinumab during Treatment Period 1 will receive secukinumab 300 mg s.c. at Week 12, Week 16 and Week 20, and placebo at Week 13, Week 14 and Week 15 to maintain the blind.

#### Figure 3-1 Study design

# 4 Rationale

# 4.1 Rationale for study design

The randomized, double-blind, parallel-group design of this study is aligned with previous studies performed in the indication of plaque psoriasis and registration secukinumab studies. The double-blind design will be maintained throughout the study to ensure reliable efficacy and safety measures are obtained for both treatment groups in patients with moderate to severe plaque psoriasis and coexisting NAFLD. This study involves 2 treatment periods, which will allow exploration of efficacy and safety effects of secukinumab 300 mg up to Week 12 in a placebo-controlled manner and additionally from Week 12 up to Week 24 (with last dose at Week 20) with active treatment only.

# 4.2 Rationale for dose/regimen and duration of treatment

Secukinumab 300 mg s.c. with an initial weekly induction schedule up to 4 weeks followed by a s.c. administration of every 4 weeks up to Week 20 is based on the secukinumab Phase 3 registration program.

The 12-week placebo-controlled Treatment Period 1 will allow indirect comparisons to placebo-controlled pivotal studies regarding skin-related endpoints which also had their primary endpoint at Week 12 and assessment of effects on NAFLD related endpoints exceeding typically observed placebo effects (Neuschwander-Tetri et al 2015, Ratziu et al 2008, Harrison et al 2018a, Harrison et al 2018b).

In previous proof-of-concept studies in NASH patients, 12 weeks has been a standard treatment length to demonstrate reduction of hepatic inflammation, steatosis and fibrosis markers, and effects have been observed as early as after 4 weeks of treatment (Neuschwander-Tetri et al 2015, Ratziu et al 2008, Harrison et al 2018a, Harrison et al 2018b). As due to ethical reasons, the placebo-controlled period needs to be limited to 12 weeks in patients with moderate to severe psoriasis, Treatment Period 2 will enable this study to explore the longitudinal effects of secukinumab up to 24 weeks. Moreover, with Treatment Period 2, all patients enrolled in the study will be able to benefit from secukinumab treatment.

# 4.3 Rationale for choice of control drug (placebo)

A placebo control has been selected for the first 12 weeks in this study in order to assess the safety and effectiveness of secukinumab 300 mg in a double-blind, unbiased manner in patients with moderate to severe psoriasis and concomitant NAFLD. Patients assigned to placebo will switch to active treatment with secukinumab 300 mg for Treatment Period 2 (Week 12 up to Week 20). Furthermore, patients will be allowed to use concomitant potent topical corticosteroids and/or vitamin D analogues as needed at the discretion of the investigator.

# 4.4 **Purpose and timing of primary analysis/design adaptations**

The primary analysis for this study will be conducted after all patients have completed Treatment Period 1. Following an evaluation of these data by a Study Steering Committee, it

Novartis	Confidential	Page 22
Protocol (Version No. 01)		Protocol No. CAIN457ADE15

will be decided whether the study will be amended to include an additional part enrolling patients with NAFLD without coexisting psoriasis.

## 4.5 Risks and benefits

Based on the therapeutic efficacy and safety in 4 pivotal randomized Phase 3 studies with dosages of 300 mg or 150 mg (Langley et al 2014, Blauvelt et al 2015, Paul et al 2015, Thaci et al 2015) secukinumab was approved to treat adults with moderate-to-severe plaque psoriasis by the FDA and the EMA in 2015. Nasopharyngitis, headache, and upper respiratory tract infection were the most common AEs and were more frequent in the secukinumab arms (mostly mild or moderate). Injection-site reactions were rare and mostly mild or moderate. A similar safety profile has been obtained with dosages of 300 mg, 150 mg or 75 mg secukinumab in a randomized Phase 3 trial in patients with psoriatic arthritis (Mease et al 2015, Mc Innes et al 2015). No cumulative or unexpected safety concerns have been identified through 5 years of treatment in the extension phase of the SCULPTURE study (Bissonnette et al 2015). Overall, serious adverse events (SAEs) occurred at similar low incidences across treatments during the first 12-week and the entire 52-week treatment periods in a pooled analysis of 10 Phase 2 and 3 studies with few AEs leading to discontinuation (Van de Kerkhof et al 2016).

Although not pre-specified in the trial protocols for secukinumab above it can be assumed from the epidemiological association that a substantial proportion of the recruited psoriasis patients suffered from concomitant NAFLD. When reported, a mean body mass index (BMI) of 28-34 kg/m^2 clearly illustrates the dysmetabolic condition of the included patients (Langley et al 2014, Paul et al 2015, Thaci et al 2015). No major liver-related events or deterioration in liver laboratory assessments have been reported to date in Phase 2 and 3 secukinumab trials. With this information from almost 4000 psoriasis patients, half of them putatively with concomitant NAFLD, it appears acceptable to rate the risk of unexpected AEs or SAEs as relatively low. In addition, one preclinical study shows that IL-17 inhibits adipogenesis, moderates adipose tissue accumulation and contributes to control glucose metabolism at least in mice und high fat diet (Zuniga et al 2010).

Fatty liver disease represents a globally increasing health threat. In particular, steatohepatitis (NASH) with accompanying inflammation contributes to the development of progressive liver damage and sometimes end stage liver failure. End stage liver damage is characterized by the development of liver cirrhosis and hepatocellular carcinoma (HCC) as the most life-threatening complication. There is no established therapy with proven long-term success and absent risk profile so far. Given the fact that a therapy with secukinumab in a dosage

according to the label represents a convenient and safe intervention in patients with plaque psoriasis, the conduction this study in psoriasis patients with concomitant NAFLD is justified to treat a frequently coinciding disease of global socioeconomic impact and disease burden with life-threatening complications of end stage disease.

The risk to patients in this trial may be minimized by compliance with the eligibility criteria and study procedures, as well as close clinical monitoring.

Women of childbearing potential must be informed that taking the study treatment may involve unknown risks to the fetus if pregnancy were to occur during the study, and agree that in order to participate in the study they must adhere to the contraception requirements outlined in the exclusion criteria. If there is any question that the patient will not reliably comply, they should not be entered or continue in the study.

# 5 Population

Approximately 90 patients with moderate to severe plaque psoriasis and coexisting NAFLD who are candidates for systemic psoriasis therapy will be included in this study.

# 5.1 Inclusion criteria

Patients eligible for inclusion in this study must meet **all** of the following criteria:

- 1. Patient must be able to understand and communicate with the investigator and comply with the requirements of the study, and must provide written, signed and dated informed consent before any study assessment is performed.
- 2. Men and women  $\geq 18$  years of age at the time of consent.
- 3. Moderate to severe plaque-type psoriasis diagnosed for at least 6 months prior to Screening with a PASI of >10 at baseline.
- 4. Candidate for systemic therapy, defined as a subject having moderate to severe chronic plaque-type psoriasis that is inadequately controlled by:
  - Topical treatment and/or,
  - Phototherapy and/or,
  - Previous systemic therapy.
- 5. Diagnosis of NAFLD by either ultrasound at Screening or liver histology within 6 months before Baseline.
- 6. Obesity with BMI > 25 kg/ m^2 at Screening.
- 7. Elevation of ALT 1.2 to  $3.0 \times ULN$ .
- Liver fat ≥ 8% at Screening as determined by the reading of the central MRI vendor of locally produced images. Note: the MRI assessment should only be performed after eligibility has been confirmed for all other Screening assessments.

# 5.2 Exclusion criteria

Patients meeting any of the following criteria are not eligible for inclusion in this study.

1. Forms of psoriasis other than chronic plaque-type psoriasis at Screening.

- 2. Drug-induced psoriasis (i.e. new onset or current exacerbation from beta-blockers, calcium channel inhibitors or lithium) at screening and baseline.
- 3. Ongoing use of prohibited treatments (see Section 6.2.2). Respective washout periods detailed in this section have to be adhered to.
- 4. History of hypersensitivity to any of the study drug constituents.
- 5. Pregnant or nursing (lactating) women.
- 6. Women of childbearing potential, defined as all women physiologically capable of becoming pregnant, unless they are using effective methods of contraception during the study or longer if required by locally approved prescribing information (e.g., 20 weeks in the European Union). Effective contraception methods include:
  - Total abstinence (when this is in line with the preferred and usual lifestyle of the patient). Periodic abstinence (e.g., calendar, ovulation, symptothermal, post-ovulation methods) and withdrawal are not acceptable methods of contraception.
  - Female sterilization (have had surgical bilateral oophorectomy with or without hysterectomy) total hysterectomy or tubal ligation at least 6 weeks before taking study treatment. In case of oophorectomy alone, only when the reproductive status of the woman has been confirmed by follow-up hormone level assessment.
  - Male sterilization (at least 6 months prior to Screening). For female patients on the study, the vasectomized male partner should be the sole partner for that patient.
  - Barrier methods of contraception: condom or occlusive cap (diaphragm or cervical/vault caps). For countries where applicable, the use of spermicidal foam/gel/film/cream/vaginal suppository will be allowed.
  - Use of oral (estrogen and progesterone), injected, or implanted hormonal methods of contraception or placement of an intrauterine device or intrauterine system or other forms of hormonal contraception that have comparable efficacy (failure rate < 1 %), for example hormone vaginal ring or transdermal hormone contraception. In case of use of oral contraception, women should have been stable on the same pill for a minimum of 12 weeks before taking study treatment.

Women are considered post-menopausal and not of childbearing potential if they have had 12 months of natural (spontaneous) amenorrhea with an appropriate clinical profile (e.g. age appropriate history of vasomotor symptoms) or have had surgical bilateral oophorectomy (with or without hysterectomy), total hysterectomy or tubal ligation at least 6 weeks ago. In the case of oophorectomy alone, only when the reproductive status of the woman has been confirmed by follow-up hormone level assessment, is she considered not of childbearing potential.

- 7. Previous treatment with biological drug targeting IL-17 or the IL-17 receptor (including prior treatment with secukinumab, ixekizumab, or brodalumab).
- 8. Past medical history record of infection with human immunodeficiency virus (HIV), hepatitis B or hepatitis C prior to screening.
- 9. Active systemic infections during the last two weeks (exception: common cold) prior to randomization or any infection that reoccurs on a regular basis.
- 10. History of an ongoing, chronic or recurrent infectious disease, or evidence of tuberculosis infection as defined by a positive QuantiFERON-TB Gold Plus (QFT) test at screening.

Subjects with a positive or indeterminate QFT test may participate in the study if full tuberculosis work up (according to local practice/guidelines) was completed within 12 weeks prior to randomization and establishes conclusively that the subject has no evidence of active tuberculosis. If presence of latent tuberculosis is established, then treatment according to local guidelines must have been completed prior to screening. During treatment of latent tuberculosis, ALT had to remain below 2x compared to pre-treatment ALT value.

11. Significant medical problems, including but not limited to:

- Congestive heart failure [New York Heart Association status of class III or IV].
- Severely reduced kidney function (estimated glomerular filtration rate (eGFR)  $\leq 29 \text{ mL/min}/1.73\text{m}^2$ ).
- 12. Unstable weight ( $\pm$  5%) over the last 6 months prior to Screening.
- 13. Type I diabetes, or uncontrolled Type II diabetes (defined as HbAlc  $\geq$  10 % at screening).
- 14. Total white blood cell (WBC) count  $<2500/\mu L$ , or neutrophils  $<1500/\mu L$  or hemoglobin <8.5 g/dL at Screening.
- 15. Evidence of hepatic decompensation or severe liver impairment or cirrhosis, as defined by the presence of any of the following abnormalities:
  - Serum albumin < 3.2 mg/dL
  - INR > 1.3
  - Total bilirubin > 1.3 mg/dL
  - AST > 5x ULN [for elevation of ALT refer to inclusion criterion 7]
  - Alkaline phosphatase > 300 IU/L
  - Platelets outside of normal reference range  $(\pm 5\%)$
  - History of esophageal varices, ascites, or hepatic encephalopathy
  - Splenomegaly
- 16. History of liver transplantation or planned liver transplant.
- 17. History of biliary diversion.
- 18. Presence or history of other liver disease (including but not limited to autoimmune hepatitis, hereditary hemochromatosis, alpha-1-antitrypsin deficiency, Wilson's disease, drug-induced liver disease).
- 19. Current, or history of, significant alcohol consumption for a period of more than 3 consecutive months within 1 year prior to screening (significant alcohol consumption is defined as more than 20 g/day in females or more than 30 g/day in males, on average) or a score on the modified alcohol use disorders identification test (AUDIT) questionnaire  $\geq 8$ .
- 20. History of bariatric surgery or intention to have bariatric surgery during study conduct.
- 21. History of lymphoproliferative disease or any known malignancy or history of malignancy of any organ system treated or untreated within the past 5 years, regardless of whether there is evidence of local recurrence or metastases (except for skin Bowen's disease, or basal cell carcinoma or actinic keratosis that have been treated with no evidence of recurrence in the past 12 weeks; carcinoma in situ of the cervix or non-invasive malignant colon polyps that have been removed).

- 22. Underlying conditions (including, but not limited to metabolic, hematologic, renal, hepatic, pulmonary, neurologic, endocrine, cardiac, infectious or gastrointestinal) which in the opinion of the Investigator significantly immunocompromise the patient and/or places the patient at unacceptable risk for receiving an immunomodulatory therapy.
- 23. Current severe progressive or uncontrolled disease, which in the judgment of the clinical investigator renders the subject unsuitable for the trial or puts the subject at increased risk.
- 24. Any medical or psychiatric condition, which in the investigator's opinion would preclude the participant from adhering to the protocol or completing the study per protocol.
- 25. Inability or unwillingness to undergo MRI of the abdomen (e.g., patients with pacemakers, or metal fragments / foreign objects in the body that are not compatible with performing an MRI of the abdomen, weight in excess of MRI machine capacity).
- 26. Inability or unwillingness to undergo repeated venipuncture (e.g., because of poor tolerability or lack of access to veins).
- 27. Ongoing participation (including safety follow-up period) in other interventional studies.

No additional exclusions may be applied by the Investigator in order to ensure that the study population will be representative of all eligible patients.

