#### A selection of the main changes encompasses:

- Section 5.2 Exclusion criteria:
  - Exclusion criterion 10 was modified in order to exclude patients with a positive QuantiFERON-TB-Gold Plus test in whom the presence of latent tuberculosis was established and tuberculosis treatment was not completed prior to screening. In addition, it was specified that during latent tuberculosis treatment, had to remain below 2x compared to pre-treatment ALT value.
  - Exclusion criterion 13: Definition of uncontrolled diabetes was clarified (applicable for Type II diabetes only).
  - Exclusion criterion 14 ("platelets < 100.000 /µL") was removed as this information is already included in the definition in Exclusion criterion 15.
- Section 6 Treatment:
  - In Table 6-1 (Section 6.1.1), the information on the sponsor was corrected to "Sponsor (local)".
  - Country-specific procedures for Spain e.g. for the handling of study treatment, were added to the following sections and information regarding the processes in Germany was added, if relevant:
    - Section 6.3.1 Patient numbering
    - Section 6.3.2 Treatment assignment, randomization
    - Section 6.6.2 Emergency breaking of assigned treatment code
    - Section 6.7 Preparation and dispensation
    - Section 7 Informed consent procedures
- Section 8 Visit schedule and assessment: Changes have been made to Table 8-1: it was clarified that INR is assessed only at screening visit.
- Section 8.2.2 Tuberculosis screening: This section was updated to reflect the changes of exclusion criterion 10.

- Section 8.4 Laboratory evaluations: Removal of parameters that will no longer be assessed during the study from table 8-4.
- Section 8.5.1 Alcohol use disorder identification test (AUDIT): Instead of the patients completing the questionnaire on their own, the site staff will perform the AUDIT together with the patient in the form of an interview. Consequently, AUDIT was removed from section 8.5.2 Patient reported outcomes.

Additionally, this protocol amendment includes changes to increase clarity and consistency of the text. Consequently, changes were incorporated directly into the protocol with track changes, even if not listed specifically in this section.

The changes herein do not affect the Informed Consent. None of the changes described in this amended protocol are made due to newly emerged safety considerations.

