	
 
Previous treatment with biological drug targeting IL-17 or the IL-17 receptor (including prior treatment with secukinumab, ixekizumab, or brodalumab).
 

	8. Past medical history record of infection with human immunodeficiency virus (HIV), hepatitis B or hepatitis C prior to screening.
	
 
Active systemic infections during the last two weeks (exception: common cold) prior to randomization or any infection that reoccurs on a regular basis.
 

	10. History of an ongoing, chronic or recurrent infectious disease, or evidence of tuberculosis infection as defined by a positive QuantiFERON-TB-Gold Plus (QFT) test at screening. Subjects with a positive or indeterminate QFT test may participate in the study if full tuberculosis work up (according to local practice/guidelines) was completed within 12 weeks prior to randomization and establishes conclusively that the subject has no evidence of active tuberculosis. If presence of latent tuberculosis is established, then treatment according to local guidelines must have been completed prior to screening. During treatment of latent tuberculosis, ALT had to remain below 2x compared to pre-treatment ALT value.
	11. Significant medical problems, including but not limited to:
	
 
Congestive heart failure [New York Heart Association status of class III or IV].
 

	
 
Severely reduced kidney function (estimated glomerular filtration rate (eGFR) ≤ 29 mL/min/1.73 m^2).
 

	12. Unstable weight (± 5%) over the last 6 months prior to Screening.
	
 
Type I diabetes or uncontrolled Type II diabetes (defined as HbAlc ≥ 10% at Screening.)
 

	
 
Total white blood cell (WBC) count < 2500/μL, or neutrophils < 1500/μL or hemoglobin < 8.5 g/dL at Screening.
 

	15. Evidence of hepatic decompensation or severe liver impairment or cirrhosis, as defined by the presence of any of the following abnormalities:
	
 
Serum albumin < 3.2 mg/dL
 

	• INR > 1.3
	
 
Total bilirubin > 1.3 mg/dL
 

	• AST > 5 × ULN [for elevation of ALT refer to inclusion criterion 7]

 
Alkaline phosphatase > 300 IU/L
 

 
Platelets outside of normal reference range (± 5%)
 

History of esophageal varices, ascites, or hepatic encephalopathy
Splenomegaly
16. History of liver transplantation or planned liver transplant.
17. History of biliary diversion.

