#### Liver function and related variables

ALT (SGPT):	> 3 x upper limit of normal (ULN)
AST (SGOT):	> 3 x ULN
Total bilirubin:	> 1.5 x ULN
Alkaline phosphatase:	> 2 x ULN
Renal function and electrolyte variables	
Creatinine (serum):	> 1.5 x ULN
Hematology variables	
Hemoglobin:	$\geq$ 20 g/dL decrease from Baseline
Platelet count:	< lower limit of normal (LLN)
White blood cell count:	< 0.8 x LLN
Neutrophils:	< 0.9 x LLN
Eosinophils:	> 1.1 x ULN
Lymphocytes:	> 1.1 x ULN
Urinalysis variable	
Protein urine dipstick:	++* (* ++ is $\geq 100 \text{ mg/dL}$ )

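### Exclusion criterion 15: the albumin limit is printed in mg/dL and can exclude nobody; the platelet limit also rejects high counts and leaves the direction of its ±5% unstated

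*Protocol*

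**What the plan says.** Exclusion criterion 15 in Protocol Section 5.2 reads: "Evidence of hepatic decompensation or severe liver impairment or cirrhosis, as defined by the presence of any of the following abnormalities". One positive item is therefore enough.

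Two of the laboratory items matter here, and the protocol summary repeats both in the same terms:

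- Albumin: "Serum albumin < 3.2 mg/dL".
- Platelets: "Platelets outside of normal reference range", with ±5% in brackets after it.

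The other laboratory items (INR, total bilirubin, AST, alkaline phosphatase) each have a single upper limit. The list also contains splenomegaly and a history of varices, ascites or encephalopathy.

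Three other places bear on the reading. The list of main changes in Amendment 1 says that the separate exclusion for platelets below 100.000/µL "was removed as this information is already included in the definition in Exclusion criterion 15". Appendix 1 (Section 16.1) counts a platelet value as notable only when it is below the lower limit of normal. The end of Section 5.2 bars investigators from adding exclusions of their own. Section 8.4.4 assigns hematology and chemistry to a central laboratory, but neither document gives its platelet reference range.

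**The concern.** An eligibility limit has to work as printed, all the more where sites may not add exclusions. The albumin item looks inoperative. A site that applies it literally passes every patient; a site that silently reads another unit applies a rule the protocol does not contain. Either way, the item meant to catch poor synthetic function does not do so on the authority of the text.

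The platelet item has a different fault. It has two sides, in a list that otherwise gives each laboratory value one limit, so a patient whose only abnormality is a high count is labelled as having advanced liver disease. The bracketed 5% has no direction, so two sites with the same central result can decide differently. Since Amendment 1, this is also the only platelet criterion.

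At stake is whether the screened population matches the one criterion 15 describes, and whether the study report can say how the criterion was applied.

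**Working it through.** The plan states no figure on this point that could be reproduced. The check is a unit conversion plus the two readings of the 5%.

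**Albumin.** Input from Section 5.2 and the protocol summary: limit 3.2 mg/dL. Conversion: 1 g/dL = 1000 mg/dL.

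- Limit in g/dL: 3.2 / 1000 = 0.0032 g/dL.
- Assumed very low albumin, 1.0 g/dL: 1000 mg/dL; 1000 / 3.2 = 312.5 times the limit.
- Assumed 3.5 g/dL: 3500 / 3.2 = about 1094 times the limit.
- Assumed 5.0 g/dL: 5000 / 3.2 = about 1562 times the limit.

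No value in the assumed range of 1.0-5.0 g/dL comes near the limit. An extraction fault is unlikely: the same unit stands in two places, and the hemoglobin limit in criterion 14 is printed as "<8.5 g/dL at Screening".

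**Platelets, the two readings.** The documents give no reference range, so 150-400 x10^9/L is an assumption.

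- 5% widens the range: 150 × 0.95 = 142.5 and 400 × 1.05 = 420. Eligible: 142.5-420.
- 5% narrows the range: 150 × 1.05 = 157.5 and 400 × 0.95 = 380. Eligible: 157.5-380.

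Counts of 142.5-157.5 and 380-420 are eligible under one reading and excluded under the other.

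**Platelets, low counts.** The lowest lower cut over the assumed ranges 130-400, 140-400, 150-400 and 150-450 is 130 × 0.95 = 123.5. The former limit of 100.000/µL is 100 x10^9/L, so every count it excluded is still excluded under both readings.

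**Platelets, share affected.** Assume healthy values are normal and the reference range is their central 95%. For 150-400 the mean is 275 and the SD is (400 − 150) / (2 × 1.96) = 63.8.

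- Widened: below 142.5, z = −132.5 / 63.8 = −2.08, 1.9%; above 420, z = 145 / 63.8 = 2.27, 1.1%. Total 3.0%.
- Narrowed: below 157.5, z = −117.5 / 63.8 = −1.84, 3.3%; above 380, z = 105 / 63.8 = 1.65, 5.0%. Total 8.3%.

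Over the four assumed ranges the total is 3.0-3.2% when widened (high side 1.1-1.2%) and 7.9-8.3% when narrowed (high side 4.7-5.0%). These shares refer to healthy values, not to this patient group, and only show the scale of the ambiguity.

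**The case against.** The albumin line is a transparent unit slip, and few sites would apply it literally. Even read literally, INR, bilirubin, AST, alkaline phosphatase, splenomegaly and the history items each still exclude, and exclusions 22 (which names hepatic conditions) and 23 leave room for the investigator's judgement. That stands as mitigation. It does not make the limit work: a patient whose only listed abnormality is low albumin passes criterion 15 as written.

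On platelets, the bracketed 5% reads most naturally as a tolerance that widens the range. Criterion 12 uses the same notation for weight change, and central testing removes differences in measurement. That is a fair guess at the intent, but the text does not say it. The documents also give no rationale for the upper bound, so they do not show that it was unintended: Appendix 1 flags notable values and is not an eligibility rule. This is why the point asks the sponsor to reconcile the line and does not choose a cut.

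Four stronger inferences are tempting, and the documents do not support them.

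- That neither limit detects liver impairment. This is untrue for platelets, since low counts are excluded under either reading.
- That the platelet line contributed to the low recruitment named in SAP Sections 2.1 and 4. No screen failures by reason are reported.
- That about 2.5% of patients are wrongly rejected for a high count. That share belongs to an unmodified upper reference limit, and criterion 15 has no such limit under either reading.
- That patients with impaired synthetic function were in fact enrolled. No patient data are given.

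**Conclusion.** The albumin limit is wrong as printed, in both places. It excludes nobody, and this holds over the whole assumed range of 1.0-5.0 g/dL. The remaining items and exclusions 22 and 23 reduce the consequence without removing it.

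The platelet item does its job on the low side. Its faults are that an isolated high count counts as advanced liver disease and that its cut is undefined. Under the assumed reference ranges and normality, the high side covers about 1% of healthy values if the 5% widens the range and about 5% if it narrows it.

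Neither fault touches randomisation, blinding or the PASI90 and ALT analyses, and the SAP limits the stopped study to an abbreviated analysis. It is a correction to eligibility text that should be made, with a safety aspect for albumin.

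**What to change.** - Albumin: in criterion 15, in both Section 5.2 and the protocol summary, correct the unit to the one in which a value of 3.2 is meaningful for the central laboratory.
- Platelets: the sponsor should reconcile the line with the low-only flag in Appendix 1 and with the amendment's stated reason for dropping the separate low-platelet criterion. It should then state the intended direction and cut as a single expression of the central laboratory limits. Which cut is right is for the sponsor to decide.
- Because the study has stopped, carry the corrected text into any reuse of the protocol, and say in the study report how sites applied both limits. Protocol Section 8.1.1 has the reason for each screen failure recorded, and SAP Section 2.3.1 already counts screen failures, so those under criterion 15 can be listed. The laboratory listings in SAP Section 2.7.3 should show whether any treated patient had a low screening albumin.

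The cost is two wording corrections and a short statement in the report. Albumin and platelets are both already in the central laboratory panel, so no new test is needed.
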